13.3 Suspected Unexpected Serious Adverse Reactions (SUSARs)

A SUSAR is defined as a suspected, serious adverse reaction, the nature, severity, or outcome of which is not consistent with the reference safety information. '*Unexpected*' reactions are defined using the summary for product characteristics (SPC) for Solu-Medrol³². Sponsor of the trial will be registered in the EudraVigilance system prior to initiation of the trial and is responsible of reporting any SUSARs to the EudraVigilance system and the ethics committee as soon as possible, at latest 7 days following awareness of event if life-threatening. If the SUSAR is not life-threatening the event will be reported at latest 15 days following awareness of the event.

14. Finance and Insurance

This study is investigator-initiated, and the study will be funded by external foundations for medical research. No funding has been obtained at present time. Sponsor is responsible for funding the costs of the trial until funding has been achieved. When funding is achieved, the ethics committee will be noticed. The preliminary budget of the study is approximately 6.2 million DKK.

All patients participating in the trial are insured by the Patient Compensation Association and the Danish patient insurance.

15. Publication

All results (positive, negative, or inconclusive) will be published in international peer-reviewed journals. The data will also be presented at national and international congresses. No participants will be identified in any reports or publications. All analyses will be conducted by the investigators of the trial. The trial will not be unblinded until acceptance from the steering committee. The publication policy of the trial data will be uploaded to the Clinical Trials Information System (CTIS) database within one year after end of trial in accordance with Clinical Trial Regulation 536/2014 Annex IV.

The authorship order: [name] [name] will be first author and [name] [name] and [name] will be shared last author. The following authorships will be granted in according to ICMJE guidelines. However, all co-investigators will be offered authorship.

16. Annual Safety Report

Throughout the whole study, annual safety reports will be uploaded to the CTIS database every year. Annual safety reports will not be sent in the period between trial completion and the 10 years follow up on mortality and hospitalization of HF.

Appendix A (Cardiac Magnetic Resonance Protocol and Endpoints)

Purpose:

- To describe the cardiac magnetic resonance (CMR) imaging scan for the PULSE-MI trial.
- To determine final infarct size by late gadolinium enhancement (LGE) on CMR 3 months after ST-Segment Elevation Myocardial Infarction (STEMI).

Setting:

All CMR scans will be performed at Rigshospitalet, Copenhagen University Hospital, Denmark.

Key points

The CMR scanner is of 1.5 Tesla field strength with a standard phased array cardiac surface coil.

The CMR scans should be performed twice post-STEMI. The first scan will be performed within 48 hours (Acute scan), and the second scan will be performed 3 months following STEMI (Follow-up scan).

Acute scan: The acute scan will be performed preferably within 48 hours of STEMI due to logistics at Rigshospitalet, Denmark. However, there is no set upper limit to the time from index event to scan, as long as it is performed within 5 days of index event (acute phase).

Follow-up: The follow-up scan should be performed as close to 3 months following the index event as possible.

The primary endpoint of the study is final infarct size (% of the left ventricle (LV) mass) measured by LGE on CMR 10-15 minutes after gadolinium contrast (0.15 mmol/kg) is given.

CMR set-up:

CMR will only be performed in patients who have given written and oral informed consent and if no contraindications exist. The patient will undergo a CMR safety check including renal function prior to scan.

Contraindications to CMR in the study: Ferrous metal foreign body, severe claustrophobia, decreased renal function (eGFR <30 ml/min).

Patients will be profoundly prepared and informed about the CMR scan. Following the scan, patients will be briefed shortly of the findings.

CMR protocol (Acute and Follow-Up Scan):

1	Patient preparation
2	Localizers and planning
3	Cine long axis (2ch, 3ch, 4ch) Short axis (SA) localizer of ventricles and subsets (basal, mid, apical)
4	Cine para-coronal
5	T1-mapping pre-contrast (SA subsets)
6	T2* pre-contrast (full LV-coverage)
7	Contrast: 0.15 mmol/kg
8	Dynamic rest
9	Function, SSFP (SAX-stack, full LV-coverage)
10	Late gadolinium enhancement (SAX-stack, 2ch, 3ch, 4ch).
11	Aortic flow rate
12	Patient Briefing

Contrast administration:

The Intravenous contrast agent is gadobutrol (Gadovist[®], Bayer; 1.5 mmol/ml solution for injection) which will be administrated in one single-dose. The dose will be given as 0.15 mmol/kg. An automated pump injector will be used for intravenous injection of Gadovist. The amount of isotonic saline (0.9%) given with Gadovist is double the amount of contrast given (0.30 mmol/kg).

Poor breath-holding:

In patients with poor breath-holding, compressed sense sequences will be used to conduct CINE images. These sequences are free breathing.

CMR endpoints

The primary efficacy parameter for the clinical trial is the amount of *infarct size (% of LV mass)* revealed by LGE 10-15 minutes after contrast administration on CMR performed 3 months following STEMI.

Acute CMR

- Microvascular obstruction on LGE (presence/absence)
- Extent of MVO on LGE
- Infarct size on LGE
- Area at risk
- Extent of edema
- Initial myocardial salvage index (acute infarct size/area-at-risk)
- LV ejection fraction (LVEF)
- Hemorrhage

Follow-up CMR

- Final infarct size (Primary endpoint)
- Myocardial salvage index (final infarct size/area at risk)
- Change in infarct size 3 months after procedure
- LVEF
- Change from baseline LVEF to follow-up LVEF

Analyses of CMR

All analyses will be performed in Circle Cardiovascular Imaging (CVI42).

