4.1 Overall Primary Objective

To determine whether 250 mg methylprednisolone administered in the *pre-hospital* setting reduces final infarct size on CMR in patients with STEMI undergoing primary PCI.

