4.2 Secondary Objectives

- To determine whether the response of methylprednisolone differs in pre-specified sub-groups: age, gender, pre-PCI Thrombolysis in Myocardial Infarction (TIMI) flow, culprit in left anterior descending artery (LAD), time from first medical contact to primary PCI, and duration of symptoms prior to primary PCI.
- To determine whether methylprednisolone improves LVEF within 48 hours and 3 months after primary PCI.
- To determine whether methylprednisolone decreases acute infarct size and edema measured on CMR within 48 hours of primary PCI.
- To determine whether methylprednisolone decreases degree of microvascular obstruction (MVO) and hemorrhage measured on CMR within 48 hours of primary PCI.
- To determine whether methylprednisolone inhibits the inflammatory response at admission, 24 hours after admission and after 3 months. Markers of inflammation: High sensitivity C-reactive protein (hsCRP), leucocyte- and differential count, plasma cytokine levels (IL-1b, IL-2, IL-3, IL-4, IL-5, IL-6, IL-7, IL-8, IL-10, IL-12, IL-13, IL-17A, G-CSF, GM-CSF, MCP-1, MIP-1beta, INF-g and tumor-necrosis factor α (TNF- α)), and procalcitonin
- To determine whether methylprednisolone increases myocardial salvage index (MSI) on CMR
- To determine whether methylprednisolone increases coronary flow reserve (CFR) and decreases index of microcirculatory resistance (IMR).
- To determine whether methylprednisolone improves clinical outcomes (all-cause mortality and hospitalization for HF) at one year after primary PCI.
- To determine whether methylprednisolone decreases peak Troponin-T and creatine kinase myocardial band (CKMB) during admission.

All these outcomes are relevant to patients with STEMI and have the potential to change the clinical course following STEMI and standard clinical practice.

5. Endpoints and Follow-Up

Primary and secondary endpoints are listed in Table 1.

Table 1. PULSE-MI endpoints

	Intervention with glucocorticoid vs. no intervention	Timeframe
Primary endpoint	Final infarct size (% of ventricular mass) measured by LGE on CMR	3 months after primary PCI
Secondary endpoints	The extent of MVO on CMR	Within 48 hours after primary PCI
	The extent of hemorrhage on CMR	Within 48 hours after primary PCI
	Other CMR efficacy parameters as specified in the appendix A	Within 48 hours and 3 months after primary PCI
	All-cause mortality and hospitalization for HF	3 months after primary PCI

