10.1 Power Calculations

The primary endpoint is final infarct size (% of left ventricle mass) measured by LGE on CMR at 3 months. Based on results of the CMR sub-studies of the DANAMI-3 trial⁴⁰⁻⁴⁵, the mean final infarct size measured by LGE on CMR is 13% with a standard deviation (SD) of 9% in patients with STEMI. To demonstrate a relative reduction in final infarct size of 20% with a two-sided alpha level of 0.05 and a power of 80%, recruitment of 378 patients is needed. A drop-out rate of 40% is expected for the primary endpoint. Therefore, we expect to randomize 530 patients in total. However, patients will be included until 378 patients have completed the CMR at 3 months. The power calculations have been calculated by a biostatistics professor.

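### Appendix A defines both myocardial salvage indices as infarct size over area at risk, which is the unsalvaged fraction, while section 4.2 aims to increase the index

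*Protocol*

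**What the plan says.** Protocol Appendix A, under the CMR endpoints, gives the only formulas for the salvage index in either document. The acute list has "Initial myocardial salvage index (acute infarct size/area-at-risk"). The follow-up list has "Myocardial salvage index (final infarct size/area at risk").

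The intended direction is in Protocol section 4.2: "To determine whether methylprednisolone increases myocardial salvage index (MSI) on CMR". The expected direction for infarct size is the opposite. The primary objective in section 4.1 is to show that the drug "reduces final infarct size on CMR in patients with STEMI undergoing primary PCI", and section 4.2 adds "To determine whether methylprednisolone decreases acute infarct size and edema measured on CMR within 48 hours of primary PCI".

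Table 1 in section 5 does not name the salvage index. It brings the index in as a secondary endpoint through the entry "Other CMR efficacy parameters as specified in the appendix A", so the appendix is the operative definition.

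The SAP does not define the index. Its Statistical Analysis section uses area at risk only as an adjustment variable in a regression of the primary outcome. The same section sets the effect measures for efficacy outcomes: a mean difference if the outcome is treated as normal, otherwise a Wilcoxon-Mann-Whitney odds ratio, each with a 95% confidence interval.

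**The concern.** Infarct size divided by area at risk is the part of the threatened myocardium that died. The salvaged part is what remains, (area at risk − infarct size)/area at risk. The appendix therefore puts the name of one quantity on the formula of its complement, and does so for both scans. The name and the direction in section 4.2 fit the complement; the formula does not.

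An analyst who follows the appendix literally would report, under the label of salvage, an effect estimate pointing the wrong way. An analyst who uses the usual complement without comment would report an endpoint that differs from its written definition. Neither document says which to do.

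**Working it through.** **Inputs**
- Control mean final infarct size: Protocol section 10.1 states that "the mean final infarct size measured by LGE on CMR is 13% with a standard deviation (SD) of 9% in patients with STEMI".
- Target effect: a 20% relative reduction (section 10.1), so the treated mean is 13 × 0.80 = 10.4 and the difference is 2.6 points.
- Area at risk: no figure in the documents. Assumed 25% to 40% of left ventricular mass, the same in both arms and, for illustration, the same for every patient.
- Acute infarct size: no figure in the documents, so only the follow-up index can be illustrated.

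**Reproducing the plan's own figure.** The plan gives no expected value or power for the salvage index, so the check is on its numerator. With SD 9, two-sided alpha 0.05 and power 80%, the normal formula gives 2 × (1.960 + 0.842)² × 9² / 2.6² ≈ 188.1 per arm. This rounds up to 189, or 378 in total, matching section 10.1. The 13% versus 10.4% contrast is thus the one the trial was sized on.

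**The two indices.** Write IS for infarct size and AAR for area at risk.
- As written: r = IS/AAR
- Salvaged fraction: s = (AAR − IS)/AAR = 1 − r

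| Assumed AAR | r, control | r, treated | change in r | s, control | s, treated | change in s |
|---|---|---|---|---|---|---|
| 25 | 13/25 = 0.520 | 10.4/25 = 0.416 | −0.104 | 0.480 | 0.584 | +0.104 |
| 40 | 13/40 = 0.325 | 10.4/40 = 0.260 | −0.065 | 0.675 | 0.740 | +0.065 |

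At any common area at risk the written index falls by 20% in relative terms, because 10.4/13 = 0.80. The initial index has the same form, so it also falls if acute infarct size falls at an unchanged area at risk.

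**Effect on the SAP's measures.** Since s = 1 − r for each patient, a mean difference in s is minus the mean difference in r. The ranking of patients is reversed, so the Wilcoxon-Mann-Whitney odds ratio, with ties split equally, becomes its reciprocal. The standard deviation and the two-sided p-value do not change.

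**Condition on the direction.** The fall in r needs area at risk to be unchanged, or to fall proportionally less than infarct size. If both fell by 20%, an area at risk of 25 would become 20 and r would be 10.4/20 = 0.52, the same as control. Even then r remains the unsalvaged fraction. The inversion is unconditional; only the direction of movement under benefit carries the condition.

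**The case against.** The best defence is that this is a drafting slip with little reach. The name of the index and the direction in section 4.2 show what was meant. The parentheses may only indicate which infarct measurement is paired with area at risk. Appendix A also lists acute infarct size, final infarct size and area at risk as separate endpoints, so a reversed salvage result would visibly conflict with its own components. The SAP says that an overall statistical plan was published; it may define the index properly, and that cannot be checked here.

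Most of this stands as a limit on the consequences. It does not reconcile Appendix A with section 4.2, because neither document contains the other formula.

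Three stronger readings are tempting and are not supported:
- **That the reported values could not be compared with salvage indices elsewhere.** They can, after subtraction from one.
- **That an effective drug must lower the written index.** This fails if measured area at risk shrinks in proportion. The possibility is not remote, since section 4.2 also expects less edema and both edema and area at risk come from the acute scan.
- **That the trial will report benefit as harm.** The documents show what is written, not what will be computed.

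**Conclusion.** The definition is wrong as written: both indices are the complement of salvage, and section 4.2 seeks an increase in a quantity that its own hypothesis would lower. With the protocol's target effect and an assumed equal area at risk of 25% to 40% of left ventricular mass, the written follow-up index falls by 0.104 to 0.065, where true salvage rises by the same amount. Those sizes depend on the assumed area at risk and on treatment leaving it unchanged; the acute index cannot be sized from the documents.

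The damage is confined to the reported value, sign and interpretation of a secondary endpoint. A reader might infer that the trial's main conclusion or its power is at risk. Neither is: the primary endpoint is infarct size itself, the 378 patients were calculated for that endpoint, and the regression adjusted for area at risk does not use the index. This is a real error that should be corrected before analysis, but it is not critical to the trial.

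**What to change.** In Appendix A, define:
- initial index = (area at risk − acute infarct size)/area at risk
- follow-up index = (area at risk − final infarct size)/area at risk

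Repeat both formulas in the SAP and state there that a higher value is favourable. Keeping the ratio, renaming it as the unsalvaged fraction and reversing the direction in section 4.2 would also remove the contradiction, but it would drop the salvage index that the objective names.

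The cost is two lines in the appendix and a short definition in the SAP. No new scans, data or sample size calculation are needed, and any values already computed as written convert exactly by subtraction from one.

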Appendix B (End-point Definitions)

The clinical event committee (CEC) will review and adjudicate all occurrences of the clinical end-points according to the 2014 ACC/AHA Key Data Elements and Definitions for Cardiovascular Endpoint Events in Clinical Trials⁴⁶.

1. All-Cause Mortality
2. Recurrent Myocardial Infarction
3. Hospitalization for Heart Failure
4. Stroke/TIA

Mortality will to the extent possible be classified according to underlying disease. The CEC will classify the mortality as cardiovascular or non-cardiovascular death.

Cardiovascular mortality

Mortality considered as cardiovascular unless it is clearly attributable to another cause and thus includes:

- Death due to proximate cardiac cause (e.g. myocardial infarction, cardiac tamponade, worsening heart failure).
- Death caused by non-coronary vascular conditions such as neurological events, pulmonary embolism, ruptured aortic aneurysm, dissecting aneurysm, or other vascular disease.
- All procedure-related deaths, including those related to a complication of the procedure or treatment for a complication of the procedure.
- All valve-related deaths including structural or non-structural valve dysfunction or other valve-related adverse events.
- Sudden or unwitnessed death.
- Death of unknown cause.

Non-cardiovascular mortality

Any death in which the primary cause of death is clearly related to another condition (e.g. infection, cancer, suicide, accident, pulmonary, hepatobiliary, gastrointestinal, renal, overdose, neurological (excluding stroke and or cardiovascular hemorrhage of central nervous system)).

Hospitalization for heart failure is prolongation of hospitalization because of worsening of heart failure or presentation of the patient for an urgent, unscheduled clinic/office/emergency department visit or hospital admission (>24 hours), with a primary diagnosis of heart failure (HF), AND where the patient exhibits new or worsening symptoms of HF on presentation, AND has objective evidence of new or worsening HF*, AND receives initiation or intensification of treatment specifically for HF.

*Objective evidence consists of at least 2 physical examination findings OR at least 1 physical examination finding and at least 1 laboratory criterion (chest x-ray or BNP) of new or worsening HF on presentation.

Table 3. Value definition heart failure

Values	Value definition
New or worsening symptoms of HF	Dyspnea Decreased exercise tolerance Fatigue Volume overload
Objective evidence of new or worsening HF	Either at least one on physical examination: Peripheral edema Increasing abdominal distention or ascites Pulmonary rales/ crackles/crepitations Increased jugular venous pressure and/ or hepa- tojugular reflux S3 gallop Clinically significant or rapid weight gain Or at least on laboratory criterion: Biomarker increases BNP/ NT-pro BNP (> up- per reference limit). In patients with chroni- cally elevated natriuretic peptides, a significant increase above baseline is required.

	Radiological evidence of pulmonary congestion: imaging findings consistent with increased intravascular blood volume in the lungs.
Receives initiation or intensification of treatment specifically for HF	Augmentation of oral diuretic therapy Intravenous diuretic, inotrope, or vasodilator therapy Mechanical or surgical intervention including any LV assist device and mechanical fluid removal

## Statistical Analysis Plan (SAP)

The overall statistical plan was published prior to completion of the trial.

### Sample Size

The sample size was calculated based on the primary outcome of final infarct size measured by late gadolinium enhancement (LGE) on cardiac magnetic resonance (CMR) at three months. Based on results of the CMR sub-studies of the DANAMI-3 trial, the mean final infarct size measured by LGE on CMR is 13% with a standard deviation (SD) of 9% in patients with ST-segment elevation myocardial infarction (STEMI). The trial was powered to demonstrate a reduction in final infarct size of 20% with a two-sided alpha level of 0.05 and a power of 80% requiring 378 patients. A drop-out rate of 30% was expected for the primary outcome but will be adjusted according to the actual drop-out rate. Inclusion of patients will continue until 378 has completed the follow-up CMR.

### Statistical Analysis

Due to the inclusion and randomization in the prehospital setting, post-randomization exclusions of patients who do not fulfill criteria is expected. The post-randomization exclusions will include patients who are not eligible or patients with other reasons for ST-segment elevation. A differentiation between a classic type 1 acute myocardial infarction with plaque rupture and thrombosis formation and a type 2 acute myocardial infarction with other reasons for ST-segment elevation (e.g. takotsubo, myocarditis, pericarditis, spontaneous coronary artery dissection, coronary embolism, coronary spasm, anemia, etc.) can only be made after further evaluation including initial coronary angiogram and thus after inclusion. Patients included and subsequently excluded will not be included in the modified intention-to-treat population. The modified intention-to-treat population is prespecified and will not be changed during the trial.

Analyses for the primary and secondary outcomes will be performed in the modified intention-to-treat population. Thus, safety including adverse events and serious adverse events and reactions will be assessed in all randomized patients which will be included in the Supplemental Material. Safety in all randomized patients will be further analyzed by calculating a cumulative incidence curve of all-cause mortality at three months which will be included in the Supplemental Material.

The primary outcome will be tested for normality using Q-Q plot to identify if the observed data is approximate to the expected data. If the primary outcome is normally distributed, mean and standard deviation (SD) will be presented using a Student's t-test to test for differences between treatment groups, whereas median and interquartile range (IQR) and Wilcoxon Rank Sum test will be used if the primary outcome is not normally distributed. Each continuous secondary outcome will be tested for normality and will be presented as either mean and SD or median and IQR. Categorical outcomes will be presented as frequencies and percentages. To assess safety in all randomized patients, the cumulative incidence of adverse events, serious adverse events, and serious adverse reactions will be tested for differences between groups using Chi-Square or Fisher's exact test. Cumulative incidence curve will be calculated for all-cause mortality. Using a Fine and Gray model, hospitalization for heart failure will be analyzed with death considered as a competing risk.

Reporting of effect sizes was not prespecified in the protocol. For effect sizes of efficacy outcomes, mean differences with 95% confidence interval (CI) will be calculated if parametric. For non-parametric numeric outcomes, Wilcoxon-Mann-Whitney odds ratio will be calculated including 95% CI (ties are equally split between groups). To present a change in percent, the effect size for troponin-T and creatine kinase-MB will be calculated using linear regression following log transformation. The effect size of categorical efficacy outcomes will be calculated as relative risk ratios and the 95% CI will be calculated using the Wald method. For all-cause mortality and hospitalization for heart failure, the relative risk will be calculated using Cox proportional hazard analysis and presented as hazard ratios with 95% CI. Hospitalization for heart failure will be calculated with death considered as a competing risk.

In the prespecified subgroup analyses of the primary outcome, mean with standard deviation or median and IQR if non-normally distributed will be given for each group. Mean difference or Wilcoxon-Mann-Whitney odds ratio with 95% CI will be used to elucidate the effect size on the primary outcome in each subgroup. A prespecified linear regression analysis of the primary outcome will be evaluated adjusting for the area at risk in the acute cardiac magnetic resonance scan and tested for interaction with the treatment allocation.

Secondary efficacy outcomes in patients assessed for the primary outcome will be presented in a Supplementary Table. To elucidate potential differences between patients who were assessed for the primary and secondary outcomes and patients who were not, baseline tables stratified by competition of acute and follow-up CMR will be included as a sensitivity analysis in the Supplemental Material.

The P-value of the primary outcome will be two-sided and will be considered statistically significant if less than 0.050. All statistical analyses will be performed in R Studio, version 4.3.2 (RStudio Team [2020]. RStudio: Integrated Development for R. RStudio, PBC, Boston, MA; URL: <http://www.rstudio.com/>) using extension packages *survival* and *effectsize*.

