8.3 Randomization

Randomization of the patient will take place in the *pre-hospital* setting. Patients who satisfy all the eligibility requirements will be randomized. Randomization is done by the paramedic in the ambulance. Patients will be randomized in a 1:1 ratio to either infusion of 250 mg methylprednisolone or placebo that are placed in identical boxes. The paramedic randomizes the patient by picking a random box stored in the ambulance delivered by the pharmacy, including methylprednisolone or placebo, and administers (over a period of 5 minutes) the content by a bolus infusion. Following infusion of the randomized treatment, the ambulance will bring the box to the hospital alongside with ECGs obtained in the ambulance in case of emergency unblinding. All boxes are identical and has a unique box serial number. Once a patient has been randomized, the patient is considered enrolled and included in the study. The box serial number is not necessarily the same as the patient identification number. In case of any technical issues, the responsible Ph.D. student or other investigators from the steering committee will be available.

All including RD's at Rigshospitalet, legally designated representative, and paramedics have relevant knowledge of the study from the handing out of the study protocol, protocol summaries, and pocket cards as well as via e-mail and on-going project recaps. None of the including RDs, legally designated representative, or paramedics are involved with the trial except for screening, enrollment, and inclusion of the patients.

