10.3 Pre-specified Subgroup Analyses

The primary endpoint will be compared between treatment groups in pre-specified subgroup analyses: age, gender, pre-PCI TIMI flow, culprit in LAD, time from first medical contact to primary PCI, and duration from symptom to primary PCI. These subgroups will be analyzed using interaction tests. The pre-specified subgroups are factors that are known to influence the clinical course in patients with STEMI.

11. Sub-study

Prior studies have shown that reperfusion injury following primary PCI in patients with STEMI is equivalent to damage in the microcirculation causing microvascular dysfunction. The microvascular function can be investigated by thermodilution-derived parameters including CFR and IMR as well as absolute flow and absolute resistance. Prior studies in STEMI patients have shown that IMR has a prognostic value and correlates to MVO. Glucocorticoid may limit reperfusion injury by decreasing the inflammatory response in direct proximity to the microcirculation. To investigate this hypothesis, we will measure CFR and IMR on eligible patients included in PULSE-MI directly after initial primary PCI but before the catheter is removed.

CFR and IMR is measured by a pressure gauge wire and a 2-minute infusion of adenosine. This procedure will only prolong the normal PCI by 5 minutes and does not add any additional risk to the procedure and does not increase the risk of complications. The patient may experience a brief

feeling of shortness of breath during the infusion of adenosine but is not associated with other complications or side effects. Adenosine is often used in standard coronary angiography (CAG) and PCI procedure.

12. Data Storing and Handling of Personal Data

All study data will be stored pseudo-anonymously for 25 years. Data of the included patients with STEMI will be stored at an electronic database, RedCap, where data will be blinded, and patients will be identified by a study identification number only. Study participation will be annotated in the medical record of the patient.

13. Assessments of Safety and Harm

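### The primary comparison of infarct size is unadjusted although usable pre-treatment covariates are collected: valid, but precision is given up

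*SAP*

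**What the plan says.** The SAP (Statistical Analysis) gives the primary test two branches, chosen by a Q-Q plot. If the outcome looks normal, it is a Student's "t-test to test for differences between treatment groups", with a mean difference as effect size. Otherwise the "Wilcoxon Rank Sum test will be used if the primary outcome is not normally distributed", with a Wilcoxon-Mann-Whitney odds ratio. Neither branch has covariates. Protocol 10.2 says only that parametric or non-parametric methods will be used as appropriate.

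Protocol 10.3 lists age, gender, TIMI flow before PCI, LAD culprit and two time intervals ending at primary PCI. It uses them only for subgroup interaction tests and justifies them thus: "The pre-specified subgroups are factors that are known to influence the clinical course in patients with STEMI".

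The SAP does plan one adjusted model of the primary outcome: a linear regression on area at risk from the acute CMR, with a treatment interaction. It is not the primary test.

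On allocation, Protocol 8.3 says "Patients will be randomized in a 1:1 ratio" and "The paramedic randomizes the patient by picking a random box stored in the ambulance". Protocol 8.5 adds that the pharmacy and its independent statistician allocate by random number generator. No stratification factor is stated.

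**The concern.** When an outcome depends partly on things known before treatment, an unadjusted comparison leaves that variation in the error term. Here the sample size is set at 80% power with no margin, and recruitment stops at 378 completed follow-up scans, so further precision has to come from the analysis. Chance imbalance in, say, LAD culprits is not stated to be limited by design, and the primary analysis does not remove it. What is at stake is a wider confidence interval and a somewhat higher chance of missing a real effect of the planned size.

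**Working it through.** **Inputs from the documents.** The SAP (Sample Size) states that "LGE on CMR is 13% with a standard deviation (SD) of 9% in patients" and a "two-sided alpha level of 0.05 and a power of 80% requiring 378 patients". Protocol 10.1 gives the effect: "To demonstrate a relative reduction in final infarct size of 20" per cent, so the difference is 0.20 × 13 = 2.6 percentage points. Allocation is 1:1, 189 per arm.

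**Input not in the documents.** R², the share of variance in 3-month infarct size explained by pre-treatment covariates, is assumed over a range.

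**Step 1: reproduce the plan's figure.** n per arm = 2 × (1.960 + 0.842)² × 9² / 2.6² = 188.1, rounded up to 189, total 378. This matches exactly. At 189 per arm, SE = 9 × √(2/189) = 0.926, the 95% half-width is 1.96 × 0.926 = 1.81, and power is 80.2% by the normal approximation or 80.0% by the noncentral t. The stated N is therefore that of the unadjusted two-sample test.

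**Step 2: adjust.** Residual SD = 9 × √(1 − R²), SE = residual SD × √(2/189), and power is from the noncentral t with 4 degrees of freedom spent on covariates. The equivalent unadjusted N is 378 / (1 − R²).

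| Assumed R² | Residual SD | SE | 95% half-width | Power | Equivalent unadjusted N |
|---|---|---|---|---|---|
| 0 | 9.00 | 0.926 | 1.81 | 80.0% | 378 |
| 0.05 | 8.77 | 0.902 | 1.77 | 82.0% | 398 |
| 0.10 | 8.54 | 0.878 | 1.72 | 84.0% | 420 |
| 0.20 | 8.05 | 0.828 | 1.62 | 87.9% | 472 |
| 0.25 | 7.79 | 0.802 | 1.57 | 89.9% | 504 |

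The 4 degrees of freedom cost about 0.2 power points or less.

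**Step 3: what R² one covariate could give.** For a binary factor with prevalence p and a group difference of D points, R² = p(1 − p)D² / 81. With p assumed at 0.4 to 0.5, D of 3, 5 or 8 points gives R² of about 0.03, 0.07 to 0.08, or 0.19 to 0.20. LAD culprit alone could therefore be worth little or a good deal.

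**Step 4: chance imbalance.** With an assumed LAD share of 45%, the 95% range for the between-arm difference in that share is 1.96 × √(0.45 × 0.55 × 2/189) = 0.10. If LAD and non-LAD infarcts differ by 5 to 8 points, that moves the crude difference by 0.5 to 0.8 points, against a target of 2.6. The unadjusted standard error already allows for this; adjustment removes it.

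**Step 5: a skewed outcome.** A simulation of 2,000 trials of 378 patients used a gamma outcome (control mean 13, SD 9), a 20% proportional reduction and one covariate with latent R² 0.20, all but the mean, SD and reduction being assumptions. Power was 88% for the t-test, 83% for the Wilcoxon test and 94% for the adjusted linear model. Type I error was about 5% for all three. The t-test exceeds 80% here because a proportional reduction also shrinks the treated SD, to 0.8 × 9 = 7.2. The linear model thus held its error rate under this skewness.

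**Step 6: which listed factors are fixed before infusion.** The study drug is given in the ambulance. Age and sex are fixed beforehand. The culprit artery is seen at angiography, but its location was determined before infusion. Pre-PCI TIMI flow is read after infusion and is an exploratory endpoint (Protocol section 5). Both time intervals in 10.3 end at PCI, also after infusion.

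**The case against.** The strongest reply is that nothing is wrong. In a randomised trial the unadjusted test is valid, its type I error already covers chance imbalance, and the planned N matches the planned test exactly. That stands, and it limits the point to efficiency.

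A reader might infer that the listed factors are strong predictors of infarct size. The documents do not support that: 10.3 speaks of clinical course and gives no R² or correlation. At R² 0.05 the gain is only about 2 power points, and at 0 it is nil.

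A reader might also infer that the expected drop-out (40% in the protocol, 30% in the SAP) erodes the 80% power. It does not, because recruitment runs until 378 patients complete the follow-up CMR. Nor would baseline adjustment for precision cure bias from missing scans.

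It can fairly be said that an adjusted model is already planned. But the area-at-risk regression is supportive, needs an acute scan, and takes its covariate from imaging after infusion and PCI; Appendix A lists area at risk among the acute CMR endpoints, so treatment may affect it. It does not replace baseline adjustment.

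Finally, a linear model keeps the planned effect measure only in the t-test branch. In the Wilcoxon branch it would change both test and effect measure. That is correct, and the change has to be stated openly. The absence of stratification is likewise read from silence.

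**Conclusion.** The point holds as lost efficiency. Both branches of the primary test ignore pre-treatment information that the trial already collects, and prespecified adjustment would be expected to narrow the interval if that information is prognostic for infarct size. The improvement over 80% power ranges from nothing at R² 0 to about 10 points at R² 0.25. These figures rest on the plan's own 2.6-point effect, SD of 9 and 378 completers, and on an assumed R². The documents do not support reading this as bias, as an invalid test or as a trial short of its stated power. It is worth changing because the cost is small, not because the present analysis would mislead.

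**What to change.** Before unblinding, amend the SAP as follows.

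- Make the primary analysis a linear model of final infarct size on treatment, age, sex, infarct location and time from symptom onset to randomisation. Keep continuous covariates continuous and use robust standard errors.
- Name one location variable in advance: LAD culprit (already a subgroup factor) or anterior location on the pre-hospital ECG.
- Use onset-to-randomisation time in place of the intervals in 10.3 that end at PCI.
- Leave out pre-PCI TIMI flow and area at risk, both measured after infusion.
- Give a simple rule for missing covariates, such as single imputation blind to treatment.
- State that this model replaces both the t-test and the Wilcoxon branch, so that the effect measure is always the mean difference on which the sample size was built. Report the unadjusted t-test or Wilcoxon result as supportive.
- Keep the area-at-risk regression as supportive.

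The cost is about 4 degrees of freedom and a documented, justified departure from an analysis plan that the SAP says is already published. The listed factors and the qualifying ECG are already part of the trial, so no new patient measurements are needed.
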